7.10.2 Data Sets

The analyses of quality of life data will be restricted to accrued patients who have completed at least one QoL questionnaire.

7.10.3 Compliance

Compliance will be described, by time of evaluation, by the number and percentage of subjects who filled out a questionnaire (per subject, at least one question answered) in that period of evaluation. The denominator used in calculating the percentage for baseline will be all accrued subjects (**Table 48**).

7.10.4 Analyses of QOL

7.10.4.1 Baseline and Change Score Analysis

For each scale of EORTC QOL-C30 and CR29 and FIQL instrument and total score of LARS, descriptive statistics (mean, standard deviation) will be presented at baseline. The same statistics will be generated for change score from baseline at each time of post-baseline evaluation. (**Table 49** and **Table 50**)

7.10.4.2 Proportions of Deterioration and Improving or Stable for EORTC QLQ-C30 and CR29 at Post-Baseline Assessment

The deterioration is defined as a change score from baseline which is -10 points or lower. The proportions of patients who had improving (defined as change score from baseline of 10 points or higher) or stable (defined as change score from baseline of between -10 and 10 points) (**Table 51**). QoL response rate and associated 95% confidence interval will be calculated for each scale and item.

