25. Have you had difficulty remembering things?	1	2	3	4
26. Has your physical condition or medical treatment interfered with your family life?	1	2	3	4
27. Has your physical condition or medical treatment interfered with your social activities?	1	2	3	4
28. Has your physical condition or medical treatment caused you financial difficulties?	1	2	3	4

For the following questions please circle the number between 1 and 7 that best applies to you.

29. How would you rate your overall health during the past week?	1 Very Poor	2	3	4	5	6	7 Excellent
30. How would you rate your overall quality of life during the past week?	1 Very Poor	2	3	4	5	6	7 Excellent

Patients sometimes report that they have the following symptoms. Please indicate the extent to which you have experienced these symptoms during the past week.

During the past week:	Not At All	A Little	Quite a Bit	Very Much
31. Did you urinate frequently during the day?	1	2	3	4
32. Did you urinate frequently during the night?	1	2	3	4
33. Have you had any unintentional release (leakage) of urine?	1	2	3	4
34. Did you have pain when you urinated?	1	2	3	4
35. Did you have abdominal pain?	1	2	3	4
36. Did you have pain in your buttocks/anal area/rectum?	1	2	3	4
37. Did you have a bloated feeling in your abdomen?	1	2	3	4
38. Have you had blood in your stools?	1	2	3	4
39. Have you had mucus in your stools?	1	2	3	4
40. Did you have a dry mouth?	1	2	3	4
41. Have you lost hair as a result of your treatment?	1	2	3	4
42. Have you had problems with your sense of taste?	1	2	3	4
43. Were you worried about your health in the future?	1	2	3	4
44. Have you worried about your weight?	1	2	3	4
45. Have you felt physically less attractive as a result of your disease or treatment?	1	2	3	4
46. Have you been feeling less feminine/masculine as a result of your disease or treatment?	1	2	3	4
47. Have you been dissatisfied with your body?	1	2	3	4

48. Do you have a stoma bag (colostomy/ileostomy)?
(please circle the correct answer)

Yes

No

During the past week:

Not
At All A
Little Quite
a Bit Very
Much

Answer these questions ONLY IF YOU HAVE A STOMA BAG, if not please continue below:

49. Have you had unintentional release of gas/flatulence from your stoma bag?

1 2 3 4

50. Have you had leakage of stools from your stoma bag?

1 2 3 4

51. Have you had sore skin around your stoma?

1 2 3 4

52. Did frequent bag changes occur during the day?

1 2 3 4

53. Did frequent bag changes occur during the night?

1 2 3 4

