54. Did you feel embarrassed because of your stoma?

1 2 3 4

55. Did you have problems caring for your stoma?

1 2 3 4

Answer these questions ONLY IF YOU DO NOT HAVE A STOMA BAG:

49. Have you had unintentional release of gas/flatulence from your back passage?

1 2 3 4

50. Have you had leakage of stools from your back passage?

1 2 3 4

51. Have you had sore skin around your anal area?

1 2 3 4

52. Did frequent bowel movements occur during the day?

1 2 3 4

53. Did frequent bowel movements occur during the night?

1 2 3 4

54. Did you feel embarrassed because of your bowel movement?

1 2 3 4

During the past 4 weeks:

Not
At All A
Little Quite
a Bit Very
Much

For MEN only:

56. To what extent were you interested in sex? 1 2 3 4

57. Did you have difficulty getting or maintaining an
erection? 1 2 3 4

For WOMEN only:

58. To what extent were you interested in sex? 1 2 3 4

59. Did you have pain or discomfort during intercourse? 1 2 3 4

Fecal Incontinence Quality of Life Instrument

Q 1: In general, would you say your health is:

- 1 Excellent
- 2 Very Good
- 3 Good
- 4 Fair
- 5 Poor

Q 2: For each of the items, please indicate how much of the time the issue is a concern for you due to accidental bowel leakage.

Q2. Due to accidental bowel leakage:	Most of the Time	Some of The Time	A Little of the Time	None of the Time
	1	2	3	4
a. I am afraid to go out.				
b. I avoid visiting friends.	1	2	3	4
c. I avoid staying overnight away from home.	1	2	3	4
d. It is difficult for me to get out and do things like going to a movie or to church.	1	2	3	4
e. I cut down on how much I eat before I go out.	1	2	3	4
f. Whenever I am away from home, I try to stay near a restroom as much as possible.	1	2	3	4
g. It is important to plan my schedule (daily activities) around my bowel pattern.	1	2	3	4
h. I avoid traveling.	1	2	3	4
i. I worry about not being able to get to the toilet in time.	1	2	3	4
j. I feel I have no control over my bowels.	1	2	3	4
k. I can't hold my bowel movement long enough to get to the bathroom.	1	2	3	4
l. I leak stool without even knowing it.	1	2	3	4
m. I try to prevent bowel accidents by staying very near a bathroom.	1	2	3	4

Q 3: Due to accidental bowel leakage, indicate the extent to which you AGREE or DISAGREE with each of the following items.

Q3. Due to accidental bowel leakage:	Strongly Agree	Somewhat Agree	Somewhat Disagree	Strongly Disagree
a. I feel ashamed.	1	2	3	4
b. I can not do many of things I want to do.	1	2	3	4

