7.10.1.2 EORTC QLQ-CR29

QLQ-CR29 is a colon and rectum cancer site-specific supplemental module to the EORTC core questionnaire, which consists of five Functional Scales, 18 Symptoms Scales as well as stoma status. Each scale in the questionnaire will be scored (0 to 100) according to the EORTC recommendations in the EORTC QLQ-CR29 Scoring Manual. The scoring method for EORTC QLQ-CR29 is summarized below. In this summary Qi refers to the i-th question on the QLQ-CR29.

Functional scale's scores:

- Body image: $(1 - ((Q45+Q46+Q47)/3 - 1)/3) * 100$
- Anxiety: $(1 - (Q43-1)/3) * 100$
- Weight: $(1 - (Q44-1)/3) * 100$
- Sexual Interest (men): $(1 - (Q56-1)/3) * 100$
- Sexual Interest (women): $(1 - (Q58-1)/3) * 100$

Symptom scale's scores:

- Urinary frequency $((Q31+Q32)/2-1)/3 * 100$
- Blood and mucus in stool $((Q38+Q39)/2-1)/3 * 100$
- Stool frequency $((Q52+Q53)/2-1)/3 * 100$
- Urinary incontinence $(Q33-1)/3 * 100$
- Dysuria $(Q34-1)/3 * 100$
- Abdominal pain $(Q35-1)/3 * 100$
- Buttock pain $(Q36-1)/3 * 100$
- Bloating $(Q37-1)/3 * 100$
- Dry mouth $(Q40-1)/3 * 100$
- Hair loss $(Q41-1)/3 * 100$
- Taste $(Q42-1)/3 * 100$
- Flatulence $(Q49-1)/3 * 100$
- Fecal incontinence $(Q50-1)/3 * 100$
- Sore skin $(Q50-1)/3 * 100$
- Embarrassment $(Q54-1)/3 * 100$
- Stoma care problems $(Q55-1)/3 * 100$
- Impotence $(Q57-1)/3 * 100$
- Dyspareunia $(Q59-1)/3 * 100$
- Stoma status $(Q48-1) * 100$

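### CR29 bowel items are worded differently once a patient has a stoma, but the SAP pools their change scores and leaves stoma-care problems with essentially no post-baseline result

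*SAP*

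**What the plan says.** The questionnaire in Protocol Appendix V branches after item 48, which asks whether the patient has a stoma bag. One block is introduced by "Answer these questions ONLY IF YOU HAVE A STOMA BAG, if not please continue below" and runs from item 49 to item 55. The other is introduced by "Answer these questions ONLY IF YOU DO NOT HAVE A STOMA BAG" and runs from item 49 to item 54. The two blocks share item numbers but not wording. Item 52, for example, is "Did frequent bag changes occur during the day" in the first and "Did frequent bowel movements occur during the day" in the second. Item 55, "Did you have problems caring for your stoma", appears only in the stoma block.

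SAP 7.10.1.2 describes CR29 as a module "which consists of five Functional Scales, 18 Symptoms Scales as well as stoma status". It prints one formula per scale, with no separate treatment by stoma status. Item 48 is scored as a scale of its own and conditions nothing else.

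For results, SAP 7.10.4.1 gives mean and standard deviation at baseline and then: "The same statistics will be generated for change score from baseline at each time of post-baseline evaluation". SAP 7.10.4.2 classifies those changes at 10 points. Tables 49 to 51 follow this pattern: baseline, change, change category. Protocol 13.6 plans the same kinds of output. Only LARS gets an observed post-baseline summary, the severity groups in Table 52.

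**The concern.** Patients enter with an untreated tumour suitable for local excision, so nearly all should answer the non-stoma block at baseline. Those who go on to TME stay in quality-of-life follow-up, with visits timed from the TME date, and some will then answer the stoma block. Their change on five scales is a later answer about a bag minus an earlier answer about the back passage or bowel movements. The plan averages that difference with everyone else's and sorts it into improved, stable or deteriorated.

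The one scale that asks directly about managing a stoma cannot be expressed as a change at all when there was no stoma at baseline, and the SAP offers no other output for it.

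Protocol 2.0 bases the quality-of-life rationale on organ sparing giving better function than radical surgery with its possible stoma. The affected records belong mostly to patients in whom organ preservation failed, so this part of the comparison most needs a clear description.

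**Working it through.** **Items against scales** (Appendix V beside SAP 7.10.1.2)

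| Item | No stoma | Stoma | SAP scale |
|---|---|---|---|
| 49 | gas, back passage | gas, bag | Flatulence |
| 50 | stool leakage, back passage | stool leakage, bag | Fecal incontinence |
| 51 | sore skin, anal area | sore skin around stoma | Sore skin (formula prints Q50) |
| 52, 53 | bowel movements, day and night | bag changes, day and night | Stool frequency |
| 54 | embarrassment, bowel movement | embarrassment, stoma | Embarrassment |
| 55 | not asked | stoma care | Stoma care problems |

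Counting the printed list reproduces the SAP's 18 symptom scales. Five rest wholly on items 49-54 and one rests on item 55. Q50 in the sore-skin formula looks like a separate slip. Items 50 and 51 both change wording, so the count of five holds either way.

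**Stoma care problems.** This is a single item. Under the missing-item rule at the end of SAP 7.10.1.4, a blank baseline makes the scale missing, so the change is undefined. Only a patient with a stoma at both baseline and the visit can enter Tables 50 and 51. Eligibility excludes prior rectal cancer treatment (Protocol 4.2.4) but does not expressly exclude a baseline stoma, so the number is near zero rather than provably zero.

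**Stoma status.** Item 48 is answered by all, is scored, and has a row in Table 49. Table 50 is to be produced for every CR29 scale and item. With almost no stomas at baseline, the size of its mean change is essentially the percentage with a stoma at that visit.

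**Size of one response step.** Items run from 1 to 4 and are scored (Q − 1)/3 × 100.
- Single item: 1/3 × 100 = 33.3 points.
- One of the two stool-frequency items: 0.5/3 × 100 = 16.7 points.

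Both exceed 10 points, so a one-step difference due only to wording would change a patient's category.

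**Share of change scores crossing versions** = P(TME) × P(stoma at the visit, given TME).
- P(TME): 35% to 50%, from the 65% and 50% avoidance rates in SAP 5, taking everyone not preserved as having TME. SAP 2.2 reports that 11 of 19 first-stage patients avoided radical surgery, so 8/19 = 42% did not, which lies inside this range.
- P(stoma given TME): not in the documents. I use 25% to 75% for illustration. The 25% is borrowed from Protocol 2.0, where it is the non-sphincter-sparing rate in phase III trials of stage II/III disease. The 75% has no source.

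| | Stoma 25% | Stoma 75% |
|---|---|---|
| TME 35% | 0.35 × 0.25 = 8.75% (4.4 of 50) | 0.35 × 0.75 = 26.25% (13.1 of 50) |
| TME 50% | 0.50 × 0.25 = 12.5% (6.25 of 50) | 0.50 × 0.75 = 37.5% (18.75 of 50) |

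Applied to all 58 accrued patients, the extremes are 58 × 0.0875 = 5.1 and 58 × 0.375 = 21.75.

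**Possible effect on a mean.** If every affected patient shifted one step in the same direction on a single item, the mean change would move by 0.0875 × 33.3 = 2.9 to 0.375 × 33.3 = 12.5 points. This is a stress case; nothing in the documents says the wording effect is that large or runs one way.

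**The case against.** The strongest reply is that the SAP scores CR29 according to the EORTC scoring manual and prints its formulas as a summary of it. The two blocks are paired topic by topic: gas, leakage, skin, day and night frequency, embarrassment. The manual may intend each pair to form one scale. It is not among the documents, so a reader should not infer that the paired scores have been shown to be incomparable. What stands is that the wording differs, most plainly for bag changes against bowel movements, and that the SAP does not say how a change of stoma status is handled. Reporting only change from baseline is also the SAP's own choice, whatever the manual says about scale names.

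A reader might also infer that stoma burden appears in no result. The documents do not support that. Stoma status is tabulated, body image and the C30 scales are answered by everyone, and Table 39 lists diverting ostomy as a reoperation. The gap is confined to item 55 and to the reading of five scales.

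The upper end of the range is soft. It depends on an unsourced 75% and on temporary diversion, which Protocol 2.0 says is reversed by a second operation. After reversal the patient answers the non-stoma block again, so the share should fall at later visits.

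Finally, this is one of four instruments for a descriptive secondary endpoint. Surveillance patients who stay stoma-free are unaffected, and pre-excision changes should be too.

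**Conclusion.** The point holds in a limited form. Followed as written, the plan pools changes between differently worded questions on five of the 18 CR29 symptom scales for patients whose stoma status changes, and gives essentially no post-baseline result for Stoma care problems.

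About 9% to 38% of post-excision change scores on those five scales would be affected, if 35-50% have TME and 25-75% of those have a stoma at the visit. The second range is an illustration, not an estimate.

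A reader might go further and treat these scales as invalid for the whole cohort, or see a threat to the primary endpoint. Neither follows: patients whose stoma status does not change are compared on the same questions, and organ preservation does not use these data. Severity is minor to moderate.

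**What to change.** - In SAP 7.10.4.1 and Table 50, add observed (absolute) scores with N at months 6, 12, 24 and 36 for the five scales based on items 49-54, split by item 48 status at that visit. For patients with a stoma, add the item 55 scale in the same block.
- In SAP 7.10.4.1-7.10.4.2 and Tables 50-51, show change scores and change categories for the five scales separately for patients with unchanged and with changed stoma status, instead of pooling them.
- State beside those tables that the unchanged-status group is selected on a post-treatment outcome. Shown alone, it would leave out many of the patients in whom organ preservation failed and could make average bowel function look better than it was. The observed scores by stoma status must therefore accompany it.

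No new data are needed, because item 48 is part of the same questionnaire. The costs are an extra table block, smaller numbers per subgroup (substantially smaller if stomas are common), and an unchanged-status group that cannot be read as the whole cohort.

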13.6 Quality of Life Analysis

The quality of life of patients will be assessed using EORTC-QLQ C30 with EORTC QLQ-CR29 subscale. Scoring of the EORTC-QLQ C30 and CRC29 data will be completed following the procedures recommended by the EORTC Study Group on Quality of Life. For each domain or single item measure a linear transformation will be applied to standardize the raw score to range between 0 and 100. Questionnaire compliance rates will be ascertained at each measurement time point. Mean baseline scores for each subscale and summary scores will be calculated.

Mean change scores from baseline at each assessment time and associated standard deviation will be calculated. Standard CCTG QOL Response Analysis categorizing patients as either having improved, stable, or worsened QOL will also be performed [*Osoba 2005*]. A change score of 10 points from baseline is defined a priori as clinically relevant. For functional scales and global health status, patients will be considered to have QOL improvement if reporting a score 10-points or better than baseline at any time of QOL assessment. Conversely, patients will be considered worsened if reporting a score minus 10-points or worse than baseline at any time of QOL assessment without any improvement. Patients whose scores fall between 10-point changes from baseline at every QOL assessment will be considered as stable. In contrast to functional scales, for the determination of patient's QOL response, classification of patients into improved and worsened categories will be reversed for symptom scales. QOL response rate and associated 95% confidence interval will be calculated for each domain and item.

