7.10.1 Scoring Algorithms

7.10.1.1 EORTC QLQ-C30

The EORTC core questionnaire, QLQ-C30 (version 3.0), consists of five Functional Scales, Global Health Status, and nine Symptoms Scales. Each scale in the questionnaire will be scored (0 to 100) according to the EORTC recommendations in the EORTC QLQ-C30 Scoring Manual. The scoring method for EORTC QLQ-C30 is summarized below. In this summary Qi refers to the i-th question on the QLQ-C30.

Functional scale's scores:

- Physical functioning: $(1 - ((Q1+Q2+Q3+Q4+Q5)/5 - 1)/3) * 100$
- Role functioning: $(1 - ((Q6+Q7)/2-1)/3) * 100$
- Emotional functioning: $(1 - ((Q21+Q22+Q23+Q24)/4-1)/3) * 100$
- Cognitive functioning: $(1 - ((Q20+Q25)/2-1)/3) * 100$
- Social functioning: $(1 - ((Q26+Q27)/2-1)/3) * 100$

Global health status score:

- Global QOL: $((Q29+Q30)/2-1)/6 * 100$

Symptom scale's scores:

- Fatigue: $((Q10+Q12+Q18)/3-1)/3 * 100$
- Nausea and vomiting: $((Q14+Q15)/2-1)/3 * 100$
- Pain: $((Q9+Q19)/2-1)/3 * 100$
- Dyspnea: $((Q8-1)/3 * 100$
- Insomnia: $(Q11-1)/3 * 100$
- Appetite loss: $(Q13-1)/3 * 100$
- Constipation: $(Q16-1)/3 * 100$
- Diarrhea: $(Q17-1)/3 * 100$
- Financial difficulties: $(Q28-1)/3 * 100$

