Other ⁽¹⁾		** (**)
Drug 1 ...		** (**)
Number of patients with any anti-cancer treatment during after relapse		** (**)
Chemotherapy ⁽¹⁾		** (**)
Drug 1 ...		** (**)
Radiotherapy ⁽¹⁾		** (**)
Hormonal therapy ⁽¹⁾		** (**)
Drug 1 ...		** (**)
Immunotherapy ⁽¹⁾		** (**)
Drug 1 ...		** (**)
Other ⁽¹⁾		** (**)
Drug 1 ...		** (**)

(1) Patients could have more than one type of anti-cancer treatment.

Table 48: Compliance Rate with QoL Assessment

Dataset: All Quality of Life Evaluable Patients		
	N = **	
	N	received (%)
Baseline	**	** (**)
Pre-Excision	**	** (**)
Post-Excision		
Month 6	**	** (**)
Month 12	**	** (**)
Month 24	**	** (**)
Month 36	**	** (**)

Table 49: QoL: Summary Baseline Scores

Dataset: All Quality of Life Evaluable Patients		
EORTC QLQ-C30		
Functional scales		
Physical		
N	***	
Mean	***	
STD	***	
...	...	
EORTC QLQ-C30		
Global QOL		
N	***	
Mean	***	
STD	***	
EORTC QLQ-C30		
Symptom scales		
Fatigue		
N	***	
Mean	***	
STD	***	
...	...	
EORTC QLQ-CR29		
Functional scales		
Body Immage		
N	***	
Mean	***	
STD	***	
...	...	
EORTC QLQ-CR29		
Stoma status		
N	***	
Mean	***	
STD	***	
EORTC QLQ-C29		
Symptom scales		
Urinary frequency		
N	***	
Mean	***	
STD	***	
...	...	
LARS Score		
Total score		
N	***	
Mean	***	
STD	***	
FIQL Instrument		
Scales		
Lifestyle		
N	***	
Mean	***	
STD	***	
...	...	

Table 50: Summary QOL Change Scores from Baseline for Scale/Domain/Item at Each Time Period*

Dataset: All Quality of Life Evaluable Patients	
Scale/Domain/Item	Change Score
Pre-Excision	
N	**
Mean	**
STD	**
Post-Excision	
Month 6	
N	
Mean	**
STD	**
Month 12	
N	
Mean	**
STD	**
Month 24	
N	
Mean	**
STD	**
Month 36	
N	
Mean	**
STD	**

* Table will be provided for each of EORTC QLQ-C30/CR29 and FIQL instrument scale/domain/item and LARS total score.

Table 51: Proportion of Patients with Deterioration, Improvement or Stable EORTC QLQ-C30 and CR29 domains/items and Global QLQ scales*

All Quality of Life Evaluable Patients		N(%)
Deterioration		
Physical function		
Pre-Excision		**(**)
Post-Excision		
Month 6		**(**)
Month 12		**(**)
Month 24		**(**)
Month 36		**(**)
Improvement		
Physical function		
Pre-Excision		**(**)
Post-Excision		
Month 6		**(**)
Month 12		**(**)
Month 24		**(**)
Month 36		**(**)
Stable		
Physical function		
Pre-Excision		**(**)
Post-Excision		
Month 6		**(**)
Month 12		**(**)
Month 24		**(**)
Month 36		**(**)

* Table will be provided for each EORTC QLQ-C30/CR29 scale/domain/item

Table 52: Proportion of Patients in LARS Severity Groups

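### SAP 7.10.4.2 labels improvement and deterioration backwards on all 27 EORTC symptom scales, and scores sore skin from the leakage item; two further derivation rules need confirming

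*SAP*

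**What the plan says.** **Response labels.** SAP 7.10.4.2 states: "The deterioration is defined as a change score from baseline which is -10 points or lower". A change of +10 or more is improving, and anything between is stable. No distinction is made between functional and symptom scales. The same section adds that "QoL response rate and associated 95% confidence interval will be calculated for each scale and item", and the footnote to Table 51 says "Table will be provided for each EORTC QLQ-C30/CR29 scale/domain/item". Protocol 13.6 gives the 10-point rule for functional scales and global health, then says that "classification of patients into improved and worsened categories will be reversed for symptom scales".

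**Symptom scoring.** SAP 7.10.1.1 and 7.10.1.2 score symptom scales so that a higher answer gives a higher score, for example:

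- "Pain: $((Q9+Q19)/2-1)/3 * 100"

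**Sore skin.** SAP 7.10.1.2 has:

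- "Sore skin $(Q50-1)/3 * 100"

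The line above it scores fecal incontinence from the same item. In Protocol Appendix V, Q50 asks about stool leakage and the sore-skin question is "51. Have you had sore skin around your anal area". The stoma version has the same numbering.

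**Sexual interest.** SAP 7.10.1.2 lists it as a functional scale and scores it as one minus the scaled answer (Q56 for men, Q58 for women). The questionnaire asks how far the patient was interested in sex, from 1 (not at all) to 4 (very much).

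**Exposure.** SAP 7.4.3 measures treatment duration to the last day of drug administration plus 14 days (FOLFOX) or 21 days (CAPOX). SAP 7.4.1 takes its dates from the treatment administration section of the chemotherapy CRF. Neither says which date is meant for a drug taken by mouth for 14 days.

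**The concern.** Quality of life is a listed secondary efficacy endpoint (SAP 4.2), and better function is part of the protocol's case for organ preservation. Followed as printed, the SAP would put worsening diarrhea, fatigue, stool frequency, fecal incontinence or pain in the improvement rows of Table 51, and relief of those symptoms in the deterioration rows. The QoL response rates and their intervals would carry the same error.

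The sore-skin and sexual-interest formulas reach further, because they alter the scores themselves in Tables 49 to 51. The exposure wording could show capecitabine under-dosing in Tables 20 and 21 that did not occur.

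**Working it through.** **1. Count of symptom scales.** The SAP states 9 for the QLQ-C30 and 18 for the QLQ-CR29. Counting the formulas one by one agrees:

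| | 1 item | 2 items | 3 items | Total |
|---|---|---|---|---|
| QLQ-C30 | 6 | 2 | 1 | 9 |
| QLQ-CR29 | 15 | 3 | 0 | 18 |
| Both | 21 | 5 | 1 | 27 |

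**2. Smallest change against the 10-point threshold.** Items run from 1 to 4, so a k-item scale moves in steps of 100/(3k): 33.3 (k=1), 16.7 (k=2) and 11.1 (k=3). All exceed 10, so with complete items no non-zero change can be stable.

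**3. SAP rule against protocol rule.** Both rules were applied to every possible baseline and follow-up pair:

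| Items | Pairs | Stable under both | Opposite labels |
|---|---|---|---|
| 1 | 16 | 4 | 12 |
| 2 | 49 | 7 | 42 |
| 3 | 100 | 10 | 90 |

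The stable pairs are exactly those with no change. For example, a single item going from 1 to 2 gives +33.3: improving under the SAP, worsened under Protocol 13.6.

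**4. Sore skin.** Both scores are (Q50−1)/3×100, so they are equal in every patient, and Q51 enters no formula. If Q51 goes from 1 to 4 while leakage is unchanged, the printed formula gives a change of 0; scoring Q51 gives +100.

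**5. Sexual interest.** Answers 1, 2, 3, 4 score 100, 67, 33, 0 as written and 0, 33, 67, 100 without the one-minus. As written, complete loss of interest (4 to 1) is +100 and is labelled improving.

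**6. Capecitabine relative dose intensity (RDI).** The planned weekly dose reproduces: 1000 × 2 × 14 / 3 = 9333.3 mg/m²/week, as in SAP 7.4.3. Take n full-dose cycles without delay.

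- Cumulative dose = 28,000n mg/m².
- If the last day is the last tablet day (day 14): days = 21(n−1) + 13 + 21 = 21n + 13, so RDI = 21n/(21n+13). For n = 1, 2, 3, 4 this is 21/34 = 61.8%, 42/55 = 76.4%, 63/76 = 82.9% and 84/97 = 86.6%. Check at n = 4: 112,000 / 13.857 weeks = 8082.5, and 8082.5 / 9333.3 = 0.866.
- If the last day is day 1 of the last cycle: days = 21n and RDI = 100% throughout.

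Under the first reading a fully compliant four-cycle patient falls in the 80% to under 90% band of Table 21. Infusional fluorouracil is much less sensitive: six cycles give 84/85 = 98.8% (last day = day 2) or 84/86 = 97.7% (day 3); one cycle gives 14/15 = 93.3% or 14/16 = 87.5%.

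**The case against.** The best defence is that the plan as a whole is not wrong. Protocol 13.6 states the reversal and the SAP does not withdraw it, so programming that follows the protocol would be correct. Likewise, the SAP says the QLQ-CR29 is scored by the EORTC manual and that its formulas are only a summary, which would make the Q50 entry a one-character slip. It is true that wrong tables are not inevitable. But the SAP is the document that describes the final analysis, it cites the manual for scoring and not for the response rule, and 7.10.4.2 does not refer to Protocol 13.6. The text needs correcting either way.

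Some narrower points stand:

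- The step-size argument needs complete items. Under the SAP's half-item imputation, fatigue scored from three items at one visit and two at another can change by 16.7 − 11.1 = 5.6 points, which is stable under both rules.
- Restoring the direction does not fully restore Protocol 13.6. The protocol classifies each patient once over all assessments; the SAP and Table 51 classify visit by visit. That is a separate mismatch.
- Stoma status is outside the 27 but falls under the same one-direction rule, and its yes/no coding is not given.
- Sexual interest cannot be settled without the scoring manual, which is not among the documents.
- For exposure, adding exactly one cycle length suggests that counting from the start of the last cycle was intended. If so, there is no error. The 86.6% is also not a firm floor: a final dose on day 15 gives 84/98 = 85.7%, in the same band.
- The QoL results are descriptive, from a single arm, with no hypothesis test.

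**Conclusion.** Two parts are errors on the printed text. The response rule in SAP 7.10.4.2 contradicts Protocol 13.6 and, with complete items, gives the opposite label to every patient whose score changes on any of the 27 symptom scales. The sore-skin formula uses the wrong item and duplicates fecal incontinence.

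The other two parts are points to confirm. Sexual interest is probably scored in the wrong direction, judging by the item wording. The capecitabine duration is ambiguous: RDI for a full four-cycle course is 86.6% with last-tablet dating on day 14 and 100% with cycle-start dating, assuming full dose and no delay. How many patients received CAPOX is not stated, so the effect on Tables 20 and 21 cannot be sized.

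The primary endpoint and its decision rule, relapse, DFS, LARS and FIQL are not affected. The label error also leaves the mean symptom change scores in Table 50 unchanged. This should be fixed before the QoL tables are programmed.

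**What to change.** - **SAP 7.10.4.2:** state that for symptom scales and items a change of +10 or more is deterioration and −10 or less is improvement, as Protocol 13.6 requires. While editing, say whether patients are classified per visit or once over all visits, and how stoma status is handled.
- **SAP 7.10.1.2, sore skin:** score it as (Q51−1)/3×100.
- **SAP 7.10.1.2, sexual interest:** check against the cited scoring manual and state the direction. On the item wording, (Q56−1)/3×100 and (Q58−1)/3×100 would make a higher score mean more interest.
- **SAP 7.4.3:** define each drug's duration as day 1 of its first cycle to day 1 of the last cycle in which that drug is prescribed, plus 21 days (CAPOX) or 14 days (FOLFOX). Keep the existing limit to cycles in which the drug is prescribed, so that a drug stopped early is not charged for later cycles. Use the same cycle-start dating for the regimen duration in 7.4.1.

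The cost is a few lines of SAP text and programming. No new data are needed.
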